### 3 SYNOPSIS

**Protocol Number:**

CMO-US-EYE-0600

**Title:**

XEN-45 Gel Stent Versus Trabeculectomy in Glaucoma: Gold-standard Pathway Study (GPS)

**Study Product:**

XEN-45 Gel Stent (XEN)

**Study Centers:**

Approximately 25 to 40 sites in the United States

**Phase:**

Postmarketing

**Objective:**

To compare the effectiveness and safety of XEN to trabeculectomy in subjects with glaucoma refractory to topical medical therapy defined as intraocular pressure (IOP) not at target on 1 or more topical medications.

**Study Design:**

Multicenter, randomized, parallel-group, prospective, open-label

**Number of Subjects:**

Eyes of approximately 285 subjects (1 eye per subject) will be randomized to have approximately 256 study eyes complete the study.

**Treatment:**

XEN or Trabeculectomy

**Study Duration:**

12 months per participating study eye

**Study Methodology:**

This study will include subjects with glaucoma poorly controlled on topical therapy who are candidates for a subconjunctival drainage procedure. Subjects will be screened for enrollment and eligible candidates will be approached to ascertain interest in study participation. Subjects will be randomized at a ratio of 2:1, resulting in approximately 190 eyes being implanted with XEN and approximately 95 eyes receiving trabeculectomy. A randomized study design was chosen because it prevents selection bias in treatment assignments and produces comparable groups.

**Study Population:**

***Inclusion Criteria***

To be eligible for study entry subjects must satisfy all the following criteria in the study eye (only 1 eye will be allowed in the study):

1. Male or female subjects ages  $\geq 18$  years
2. Able to provide signed written informed consent
3. Glaucoma in which the IOP is not controlled on current topical IOP-lowering glaucoma medication
4. Best-corrected baseline Snellen visual acuity of 20/100 or better

5. Visual field mean deviation no worse than -18.0 dB (with no dense paracentral scotomas, eg, >18 dB total deviation on 1 or more of the 4 paracentral points)
6. Medicated IOP  $\geq 15$  mm Hg and  $\leq 44$  mm Hg on at least 1 topical IOP-lowering medication
7. Subjects not anticipated to require any other ocular surgery (eg, cataract surgery) in either eye up to 3 months from the time of inclusion
8. Area of healthy, free, and mobile conjunctiva in the target area, ie, superior bulbar conjunctiva
9. Visible trabecular meshwork with Shaffer angle grade  $\geq 2$  in the target area or, in eyes with prior failed angle surgery, an open angle in the target area
10. Preoperative laser trabeculoplasty is allowed 3 or more months prior to randomization
11. Failed ab-interno canal or suprachoroidal microinvasive glaucoma surgery (MIGS) procedures (such as iStent®, gonioscopy-assisted transluminal trabeculotomy [GATT], ab-interno canaloplasty [ABiC™], Kahook Dual Blade goniotomy, etc) are allowed 3 or more months before enrollment, with the exception of CyPass® Micro-Stents, which are not allowed. Ab-interno ablative procedures (such as endoscopic cyclophotocoagulation [ECP]) are also allowed 3 or more months before enrollment.

#### **Exclusion Criteria**

Subjects will be excluded from the study if one or more of the following criteria are applicable in the study eye:

1. Subject has active neovascular, uveitic, or angle-recession glaucoma or any glaucoma associated with vascular disorders
  2. Subject has had prior ab-externo incisional glaucoma surgery (such as trabeculectomy, viscocanalostomy, canaloplasty, tube shunts of any type, collagen implants, etc.), conjunctival filtering surgery (such as XEN), transscleral cycloablative procedures (such as cyclophotocoagulation, micropulse cyclophotocoagulation, cryotherapy, ultrasonic circular cyclocoagulation [UC3], etc) or prior major conjunctival surgery (ie, scleral buckle)
  3. Clinically significant inflammation or infection within 30 days before the Preoperative Visit (eg, blepharitis, conjunctivitis, severe ocular surface disease, keratitis, uveitis, herpes simplex infection)
  4. Presence of conjunctival scarring or prior conjunctival surgery or other conjunctival pathologies (eg, pterygium) in the target area
  5. History of corneal surgery, corneal opacities, or corneal disease that could impact assessments/surgical outcomes in the study
  6. Central corneal thickness  $\leq 490$   $\mu\text{m}$  or  $\geq 620$   $\mu\text{m}$
  7. Subjects on systemic carbonic anhydrase inhibitors (eg, Diamox® [acetazolamide] and Neptazane® [methazolamide]) at Baseline Qualifying Visit
  8. Vitreous present in the anterior chamber
  9. Aphakia
  10. Subject has had prior intraocular surgery in either eye within  $\leq 3$  months before the Preoperative Visit (including phacoemulsification)
  11. History of complicated cataract surgery with visual impairment, vitreous loss, anterior chamber intraocular lens (ACIOL), sutured intraocular lens (IOL), scleral fixated IOL or cystoid macular edema (CME), dislocated IOL
  12. Presence of intraocular silicone oil
  13. **Active** diabetic retinopathy, proliferative retinopathy, choroidal neovascularization, branch retinal vein occlusion, central retinal vein occlusion, geographic atrophy, or other ophthalmic disease or
-

- disorder that could confound study results or impaired episcleral venous drainage (eg, Sturge-Weber or nanophthalmos, Axenfeld-Rieger, iridocorneal endothelial [ICE] syndrome, etc)
14. Known or suspected allergy or sensitivity to drugs required for the protocol (including anesthesia), or any of the device components (eg, bovine or porcine products, or glutaraldehyde)
  15. Pregnant or nursing women and those planning a pregnancy during the study period
  16. Participation in another drug or device clinical trial that concludes within 30 days before the Preoperative Visit or that starts at any time during this study

**Primary Effectiveness Endpoint:**

Percentage of subjects achieving  $\geq 20\%$  mean IOP reduction from baseline at Month 12 on the same or fewer number of topical IOP-lowering medications, without clinical hypotony, loss of vision to count fingers, or a secondary glaucoma surgical intervention.

**Secondary Endpoints:**

**Effectiveness:**

- Mean and changes in mean IOP and number of topical IOP-lowering medications from preoperative baseline over time
- Change from baseline (medicated) in mean IOP and mean number of topical IOP-lowering medications at Month 12
- Proportion of eyes achieving specific IOP targets ( $\leq 18$  mm Hg,  $\leq 17$  mm Hg,  $\leq 16$  mm Hg,  $\leq 15$  mm Hg,  $\leq 14$  mm Hg,  $\leq 13$  mm Hg, and  $\leq 12$  mm Hg at Month 12)
- Proportion of eyes achieving specific percentage IOP lower targets from baseline ( $\geq 25\%$  to 50% in 5% increments)
- Proportion of eyes achieving  $\geq 20\%$  IOP reductions and specific IOP targets detailed above on same or lower number of topical IOP-lowering medications at Month 12
- Mean and changes in mean IOP and number of topical IOP-lowering medications from preoperative baseline over time in eyes with medicated baseline IOP  $\leq 18$  mm Hg
- Needling rates; number of needlings per eye; outcomes post needling, including mean IOP and number of medications measured by proportion of eyes achieving  $>20\%$  reduction at Month 12 on same or fewer topical IOP-lowering medications, and number of subjects not using any topical IOP-lowering medications; and antifibrotic use during needling

**Complete and qualified success:**

- Complete success (IOP  $\leq 18$  mm Hg, with 20% or greater IOP lowering from medicated baseline on no topical medications) at Month 12 (eyes with clinical hypotony will be excluded)
- Qualified success (IOP  $\leq 18$  mmHg with 20% or greater IOP lowering from medicated baseline with topical medications) at Month 12 (eyes with clinical hypotony will be excluded)
- Medication-free eyes, mean IOP in this cohort, and proportion of eyes at specific IOPs ( $\leq 18$  mm Hg,  $\leq 17$  mm Hg,  $\leq 16$  mm Hg,  $\leq 15$  mm Hg,  $\leq 14$  mm Hg,  $\leq 13$  mm Hg, and  $\leq 12$  mm Hg at Month 12)
- Proportion of eyes achieving specific percentage IOP lower targets from baseline ( $\geq 25\%$  to 50% in 5% increments) with medication-free eyes.

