1.1.3. Secondary Endpoints

Effectiveness:

- Mean and changes in mean IOP and number of topical IOP-lowering medications from preoperative baseline over time
- Change from baseline (medicated) in mean IOP and mean number of topical IOP-lowering medications at Month 12
- Proportion of eyes achieving specific IOP targets (≤ 18 mm Hg, ≤ 17 mm Hg, ≤ 16 mm Hg, ≤ 15 mm Hg, ≤ 14 mm Hg, ≤ 13 mm Hg, and ≤ 12 mm Hg at Month 12)
- Proportion of eyes achieving specific percentage IOP lower targets from baseline ($\geq 25\%$ to 50% in 5% increments) over time
- Proportion of eyes achieving $\geq 20\%$ IOP reductions and specific IOP targets detailed above on same or lower number of topical IOP-lowering medications at Month 12
- Mean and changes in mean IOP and number of topical IOP-lowering medications from preoperative baseline over time in eyes with medicated baseline IOP ≤ 18 mm Hg
- Needling rates; number of needlings per eye; outcomes post needling, including mean IOP and number of medications measured by proportion of eyes achieving $>20\%$ reduction at Month 12 on same or fewer topical IOP-lowering medications, and number of subjects not using any topical IOP-lowering medications; and antifibrotic use during needling.

Complete and qualified success:

- Complete success (IOP ≤ 18 mm Hg, with 20% or greater IOP lowering from medicated baseline on no topical medications) at Month 12 (eyes with clinical hypotony will be excluded)
- Qualified success (IOP ≤ 18 mm Hg with 20% or greater IOP lowering from medicated baseline with topical medications) at Month 12 (eyes with clinical hypotony will be

CONFIDENTIAL

Draft Statistical Analysis Plan v2.0

XEN-45 Gel Stent

excluded)

- Medication-free eyes, mean IOP in this cohort, and proportion of eyes at specific IOPs (≤ 18 mm Hg, ≤ 17 mm Hg, ≤ 16 mm Hg, ≤ 15 mm Hg, ≤ 14 mm Hg, ≤ 13 mm Hg, and ≤ 12 mm Hg at Month 12)
- Proportion of eyes achieving specific percentage IOP lower targets from baseline ($\geq 25\%$ to 50% in 5% increments) with medication-free eyes.

Intraoperative adjunctive antifibrotic therapy administered:

- Compound/product, mode of administration, dose and concentration, timing of adjunctive agent (surgery day and pre- and postsurgical procedure/implantation).

Visual parameters recovery post surgery:

- Mean and mean change in best corrected visual acuity (BCVA) with current glasses (preoperative and postoperative Day 1; Weeks 1 and 2; and Months 1, 3, 6, 9, and 12)

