 - $\geq 20\%$ IOP reductions at Month 12
 - IOP value of ≤ 15 mmHg at Month 12
 - Same or lower in number of topical IOP-lowering medications at Month 12 compared to the baseline
- Proportion of participants meeting all following criteria:

CONFIDENTIAL

Draft Statistical Analysis Plan v2.0

XEN-45 Gel Stent

- $\geq 20\%$ IOP reductions at Month 12
- IOP value of ≤ 14 mmHg at Month 12
- Same or lower in number of topical IOP-lowering medications at Month 12 compared to the baseline
- Proportion of participants meeting all following criteria:
 - $\geq 20\%$ IOP reductions at Month 12
 - IOP value of ≤ 13 mmHg at Month 12
 - Same or lower in number of topical IOP-lowering medications at Month 12 compared to the baseline
- Proportion of participants meeting all following criteria:
 - $\geq 20\%$ IOP reductions at Month 12
 - IOP value of ≤ 12 mmHg at Month 12
 - Same or lower in number of topical IOP-lowering medications at Month 12 compared to the baseline
- Needling rates, number of needlings per eye, outcomes post needling, including mean IOP and number of medications measured by proportion of eyes achieving $>20\%$ reduction at 12 months on same or fewer topical IOP-lowering medications, and number of patients not using any topical IOP-lowering medications, antifibrotic use during needling

Complete and qualified success:

- Proportion of participants with complete success at Month 12 which is defined as meeting all following criteria in the study eye
 - IOP ≤ 18 mmHg at Month 12
 - $\geq 20\%$ reduction in IOP from medicated baseline, which is the IOP value at Baseline Qualifying Visit, at Month 12
 - No topical medications at Baseline Qualifying Visit
 - No clinical hypotony

The topical medication includes any topical ophthalmic medication used on the study eye regardless of the indication and dosage.

This endpoint will be analyzed among the participants without topical medication at Baseline Qualifying Visit.

- Proportion of participants with qualified success at Month 12 which is defined as meeting all following criteria in the study eye
 - IOP ≤ 18 mmHg at Month 12
 - $\geq 20\%$ reduction in IOP from medicated baseline, which is the IOP value at Baseline Qualifying Visit, at Month 12
 - Taking topical medications at Baseline Qualifying Visit
 - No clinical hypotony

CONFIDENTIAL

Draft Statistical Analysis Plan v2.0

XEN-45 Gel Stent

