The topical medication includes any topical ophthalmic medication used on the study eye regardless of the indication and dosage.

This endpoint will be analyzed among the participants with topical medication at Baseline Qualifying Visit.

- Proportion of participants with IOP value of ≤ 18 mmHg at Month 12 in medication-free eye
- Proportion of participants with IOP value of ≤ 17 mmHg at Month 12 in medication-free eye
- Proportion of participants with IOP value of ≤ 16 mmHg at Month 12 in medication-free eye
- Proportion of participants with IOP value of ≤ 15 mmHg at Month 12 in medication-free eye
- Proportion of participants with IOP value of ≤ 14 mmHg at Month 12 in medication-free eye
- Proportion of participants with IOP value of ≤ 13 mmHg at Month 12 in medication-free eye
- Proportion of participants with IOP value of ≤ 12 mmHg at Month 12 in medication-free eye

- Proportion of eyes achieving specific percentage IOP lower targets from baseline (≥ 25 -50% in 5% increments) with medication-free eyes

Note: medication-free eye at Month 12 is defined as no IOP-lowering medication was used to the study eye at Month 12.

Intraoperative adjunctive antifibrotic therapy administered:

- Compound/product, mode of administration, dose and concentration, timing of adjunctive agent (surgery day and pre- and postsurgical procedure/implantation)

Note: The data will be presented only if they are collected on CRF.

Visual parameters recovery post surgery:

- Mean and mean change in best corrected visual acuity (BCVA) with current glasses (preoperative and postoperative Day 1, Weeks 1 and 2, and Months 1, 3, 6, 9, and 12)
- Mean and mean change in manifest refraction (baseline and postoperative Months 1, 3, 6, and 12)
- Mean and mean change in surgically induced astigmatism (autorefractor reading [preoperative and postoperative Months 1, 6, and 12] and, at selected sites, topography [preoperative and postoperative Week 1 and Months 1 and 12])
- Mean and mean change in optical biometry (anterior chamber depth and keratometric values [preoperative and postoperative Day 1 and Week 2]) at selected sites.

CONFIDENTIAL

Draft Statistical Analysis Plan v2.0

XEN-45 Gel Stent

Other:

- Bleb photography (anterior segment optical coherence tomography [AS-OCT] and slit lamp photography at selected sites).

Safety:

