5.4.2.1. Main Analytical Approach

All secondary endpoints will be analyzed using ITT population except for safety endpoints and PRO, which will be done using safety population.

.

All secondary endpoints in Section 5.4.2. will be summarized with descriptive statistics except for the endpoints referring to effectiveness and success (complete and qualified) .

These endpoints regarding complete/qualified success will be analyzed as follows:

For categorical secondary endpoints, the proportion of each treatment group will be computed and the 95% CI of difference between treatment groups will be computed using normal approximation.

For continuous secondary endpoints that is defined for one timepoint, the least squares mean change from baseline and the least squares mean difference between the treatment groups will be estimated using the analysis of covariance model with treatment as the factor, and baseline as a covariate variable. For continuous secondary endpoints that is defined for over time, the least squares mean change from baseline and the least squares mean difference between the treatment groups will be estimated using or mixed effects model repeated measure with treatment, time as the factor, treatment by time interaction and baseline as a covariate variable.

CONFIDENTIAL

Draft Statistical Analysis Plan v2.0

XEN-45 Gel Stent

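### Qualified success sets no limit on the number of drops, and where it is defined by drops at Month 12 it leaves out every drop-free success

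*Protocol*

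**What the plan says.** **Protocol (Synopsis and 7.2).** Both success categories require IOP of 18 mm Hg or less. Complete success is "with 20% or greater IOP lowering from medicated baseline on no topical medications) at Month 12"; qualified success is "with 20% or greater IOP lowering from medicated baseline with topical medications) at Month 12". The number of medications is not limited. By contrast, the primary endpoint must be met "on the same or fewer number of topical IOP-lowering medications, without clinical hypotony". For complete and qualified success, Protocol 11.1.3 plans a proportion and 95% CI and mentions no between-arm difference.

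**SAP 1.1.3** repeats the protocol wording for qualified success: "20% or greater IOP lowering from medicated baseline with topical medications) at Month 12".

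**SAP 5.4.2**, which lists the criteria to be analysed, moves the medication condition to baseline. Its criteria for qualified success are IOP of 18 mm Hg or less, a reduction of at least 20% from medicated baseline, no clinical hypotony, and "Taking topical medications at Baseline Qualifying Visit". It adds: "This endpoint will be analyzed among the participants with topical medication at Baseline Qualifying Visit". Complete success is the mirror image, requiring no topical medication at that same visit. Neither list has a condition on Month 12 medication.

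**SAP 5.4.2.1** then plans, for the success endpoints: "For categorical secondary endpoints, the proportion of each treatment group will be computed and the 95% CI of difference between treatment groups".

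**SAP 1.1.4 and 5.5** add Kaplan-Meier analyses of time to complete and time to qualified success, with the definitions taken from 1.1.3.

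**The concern.** There are two separate issues.

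1. **No limit.** The trial is open-label, drops are restarted on the investigator's recommendation (Protocol 8.4.5), and lowering the number of drops is part of the stated comparison (Protocol 8.1). If qualified success places no limit on drops, adding medication after a weak surgical result can turn a failure into a success.

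2. **Drop-free successes are excluded.** Under the Month 12 wording, complete and qualified success do not overlap. The qualified rate is total success minus complete success. A higher qualified rate can then mean either more eyes controlled or fewer eyes free of drops, and the number alone does not say which.

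At stake is how the reader interprets a success rate and, where 1.1.3 applies, a time-to-success curve.

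**Working it through.** The plan gives no figure for this point, so there is none to reproduce. The check is to score eyes under each definition.

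**Step 1: one eye on more drops.** Inclusion criterion 6 allows entry on one topical IOP-lowering medication. Take an eye at 25 mm Hg on 1 drop before surgery and 17 mm Hg on 3 drops at Month 12, without hypotony, vision loss or further surgery, and with the same values at both preoperative visits. The IOP change is (17 − 25)/25 = −32%.
- Primary endpoint: fails, because 3 > 1.
- Qualified success, protocol and SAP 1.1.3: met (17 ≤ 18, 32% ≥ 20%, on drops at Month 12).
- Qualified success, SAP 5.4.2: met (on drops at the Baseline Qualifying Visit).

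The missing limit therefore holds on every wording. With the SAP's 68 and 34 completers, each such eye adds 1/68 = 1.5 points or 1/34 = 2.9 points.

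**Step 2: one eye free of drops.** Take the same eye at 17 mm Hg on no drops at Month 12. It is not a qualified success under the protocol or SAP 1.1.3, but it is one under SAP 5.4.2. Because entry requires at least one drop, 5.4.2 puts essentially every eye in the qualified subset and essentially none in the complete subset.

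**Step 3: the algebra under the Month 12 wording.** Let S be total success, c complete and q qualified, so q = S − c. If S is equal in both arms, the difference in q is the difference in c with its sign reversed. For illustration, assume S = 70% in both arms and c = 35% for XEN and 50% for trabeculectomy. Then q is 35% and 20%. The 95% CIs use d ± 1.96 × √[p₁(1 − p₁)/68 + p₂(1 − p₂)/34]:
- complete: −15 points (−35 to +5)
- qualified: +15 points (−3 to +33)
- total: 0 points (−19 to +19)

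**Step 4: separating the two issues.** Assumed eyes meeting the IOP criteria: XEN 20 drop-free, 17 on the same or fewer drops, 7 on more (of 68); trabeculectomy 20, 3 and 1 (of 34).

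| Definition | XEN | Trabeculectomy | Difference, points (95% CI) |
|---|---|---|---|
| Complete, Month 12 status | 20/68 = 29.4% | 20/34 = 58.8% | −29.4 (−49.2 to −9.6) |
| Qualified, Month 12 status, no limit | 24/68 = 35.3% | 4/34 = 11.8% | +23.5 (7.8 to 39.2) |
| Qualified, Month 12 status, with limit | 17/68 = 25.0% | 3/34 = 8.8% | +16.2 (2.1 to 30.2) |
| SAP 5.4.2 as written (drop-free eyes counted, no limit) | 44/68 = 64.7% | 24/34 = 70.6% | −5.9 (−25.0 to 13.2) |
| Total success with limit | 37/68 = 54.4% | 23/34 = 67.6% | −13.2 (−32.9 to 6.4) |

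A limit alone does not remove the reversal; counting drop-free eyes does.

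**Step 5: where the Month 12 wording is actually used.** The between-arm CI in SAP 5.4.2.1 applies to the endpoints listed in 5.4.2, hence to the baseline-status definition. The time-to-event analysis points to 1.1.3, hence to the Month 12 wording applied over follow-up. There, an eye that meets the IOP criteria only while drop-free never has the event and is censored at its last known date.

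**The case against.** The strongest reply is that the planned Month 12 comparison does not have the reversal. A reader might infer that the SAP's between-arm CI will reward the arm with more eyes on drops. The documents do not support that: the definition that receives the CI is the one in 5.4.2, which counts drop-free eyes. Nor does SAP 5.4.2.1 say that a higher qualified rate is better. It gives an estimate and an interval, SAP 5.4.1 names no key secondary endpoint, and 5.4.3 has no multiplicity adjustment. This stands, and it confines the reversal to the time-to-event analysis and to any later alignment of 5.4.2 with the protocol.

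A second reply is that a limited version is already planned. SAP 5.4.2 lists a composite of at least 20% reduction, IOP of 18 mm Hg or less, and the same or fewer medications, and it counts eyes with and without drops. The primary endpoint has the limit, and medication-free eyes and change in medication number are also reported. This largely stands. The composite is not identical, however. It has no hypotony exclusion, and it refers to baseline without calling it medicated, which SAP 5.1 defines as preoperative, when drops may already have been stopped (Protocol 8.4.5).

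Third, the illustrative splits come from no document, and all three intervals in Step 3 include zero. This stands too: they show direction and mechanism, not an expected effect.

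**Conclusion.** The point holds in a limited form. No definition of qualified success limits the number of topical IOP-lowering medications, so an eye on more drops than at baseline can be counted while failing the primary endpoint. That follows from the wording and rests on no assumed rate; how many eyes it will concern is unknown.

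The reversal between arms is a property of the protocol and SAP 1.1.3 wording only. It bears on the exploratory time to qualified success, and it would enter the Month 12 comparison if 5.4.2 were brought into line with the protocol. It is also tempting to blame the reversal on the missing limit; Step 4 shows that they are independent.

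SAP 1.1.3 and 5.4.2 contradict each other on when medication status is read, and 5.4.2 together with the entry criterion leaves complete success essentially without eligible eyes. Any repair has to start there.

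Importance is low to moderate: this is a secondary endpoint with no multiplicity-controlled claim, and a similar limited composite is planned.

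**What to change.** In SAP 1.1.3, 5.4.2 and 5.5:

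1. Reconcile the sections so that complete and qualified success both use medication status at Month 12, as in the protocol. Remove the baseline-medication conditions and the two baseline-medication subsets from 5.4.2.
2. Add to qualified success that the number of topical IOP-lowering medications at Month 12 is the same as or lower than at the Baseline Qualifying Visit. In the same edit, settle which products count, because 5.4.2 currently counts any topical ophthalmic product for these endpoints, whatever its indication.
3. Give the between-arm difference and 95% CI for total success (complete or qualified) in the ITT population, with missing data handled as for the primary endpoint. Show the qualified-only share per arm descriptively.
4. Use the same total-success definition for the time-to-event analysis.

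Items 1 and 2 without item 3 would bring the reversal into the Month 12 comparison, so the changes belong together. The cost is SAP wording, one extra table row and a slightly lower qualified rate. No new data are needed.
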